**Table 2: Project Timeline**

Year	1	2	3	4	5										
Months	1-6	7-8	9-12	13-16	17-20	21-24	25-28	29-32	33-36	37-40	41-44	45-48	49-52	53-56	57-60
Start up: finalize IRB approval, finalize CRFs, train staff, create database															
New enrollment	50		100		100		50								
Follow-up															
Data analysis															
Focus groups: set up, conduct, analyze															
DSMB meets	x		x									x			

range of representative rates for those not employed. We will adjust costs for inflation using the Consumer and Medical Price Indices, as appropriate, and discount costs to the base year using a discount rate of 3%.

**D.9. Data Analysis:** We will perform descriptive analyses of all variables, then compare PA and UC groups for the adequacy of randomization, examining if covariates or baseline variables including potential moderators of the intervention and mediating relationships are equally distributed among patient groups. These baseline comparisons will be based on t-tests or Wilcoxon rank sum tests for continuous variables depending on the symmetry of the distributions, on logistic regression for binary or ordinal variables; and on Poisson log-linear regression for count data. If imbalances are found at baseline, the relevant variables will be treated as confounders in the ITT analyses and the analyses of mediators and moderators of the intervention on asthma control. To account for the potential for variation in the effectiveness of the intervention across physician practices, our analyses will compensate by including site as a fixed effect in all analyses. Analyses of PA and UC differences with respect to change from baseline at 6 and 12 months for each outcome in Aims 1 and 2 will be based on the ITT principle: all randomized subjects will be included in the analysis regardless of whether they drop out of the intervention or study. We will perform a sensitivity analysis of the missing at random assumption by following Bruce et al with a non-ignorable shared parameter model.

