The analysis will be based on random effects (RE) models applied to baseline and all follow-up visits at which outcome data are collected. The RE will be included to account for correlated and missing data. Separate time effects and time-treatment interactions will be specified for each follow-up visit, such that the treatment-time interaction for a particular visit will be the ITT effect on change since baseline. The RE models will be linear, logistic, and log-linear for continuous, binary, and count outcomes, respectively. Similar RE models will be employed for assessment of mediation and moderation in Secondary Aims 1 and 2.

**Data description, screening, and reorganization:** We will screen data for quality and integrity as proposed by Altman. For all variables we will determine measures of central tendency: mean and standard deviation for continuous variables, median and range for categorical variables. We will examine frequency distribution graphically (histograms, scatter plots) for all variables. Specific concerns will be directed to understanding the pattern of missing values, isolating outliers, confirming the homoscedasticity of observation groups, verifying the coding consistency, examining adherence to normality for variables anticipated to be so, and locating normalizing transformations for continuous variables intended to be investigated as such. For the tools we developed, we will examine internal consistency using Cronbach's  $\alpha$ .

**Addressing the impact of site on each outcome:** First, we will pool participants across sites, assuming no site effect, using logistic and regression modeling to isolate the relationship between outcome and exposure and other demographics. We have stratified randomization to analyze the effect of site. We have amplified the sample size (D.10) to have a large enough sample to conduct this analysis. As a secondary analysis, we will examine treatment-site interactions. In the presence of statistically significant interactions, we will present separate estimates of treatment effects for each site. In the case of statistically, but clinically marginally significant interactions, we will present main effect estimates of treatment effect but with interactions in the model using -1, 0, 1 dummy coding for site, so that the main effects' estimates will be for the average site.

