**Aims 1 & 2 (To assess whether PAI improves asthma control and other asthma outcomes):** The ITT effect of PA relative to UC on change in asthma control and other asthma outcomes since baseline at 6 months will be assessed with estimation and testing of the treatment-6 month visit interaction in the linear RE model (described above) with asthma control as the dependent variable. In addition, the treatment-12 month interaction will be tested and estimated to assess if the ITT effect is retained after the PA intervention ends.

**Secondary Aim 1 (Mediators):** The mediation analysis will follow the 4-step regression approach for testing mediated effects of Holmbeck. First, we will examine the association between PAI and mediators (D.8.2) by fitting separate longitudinal RE models with each mediator as the dependent variable. These models will test the effects of the PAI relative to the UC group with respect to change since baseline at each follow-up visit for the potential mediators. Second we examine the association between the PAI and asthma control as described in Aim 1. Third, we will assess the relationship between the mediators and asthma control by fitting separate longitudinal RE models with the mediators (D.8.2) as the independent variables and asthma control as the dependent variable. Finally, the mediators with significant effects at steps 1 and 3 will be included as a lagged time-varying covariate in the ITT linear RE model for asthma control in Aim 1. Mediators of the PAI will be assessed by comparing the randomization (intervention) effect estimate with and without the potential mediator in the model. A reduction of at least 15% in the treatment-visit interaction parameters at 6 and 12 months due to the inclusion of the mediator in the model will be the criteria for a significant mediator.

**Secondary Aim 2: Moderators** of the intervention (D.8.3) will be tested and estimated with 3- and 2-way interactions among the treatment factor, potential moderator, and visit factor in the ITT model in Aim 1. Similarly, moderators of the mediating relationship will be assessed with 3- and 2-way interactions among the treatment factor, mediator, potential moderator, and visit factor in the mediation model in Secondary Aim 1.

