**Specific Aim 1:** The power analysis is based on the 2-sample t-test with adjustments for 3 or 5 repeated measures per participant. The adjustment for clustering by patient multiplies the estimated sample size under simple random sampling by a design effect,  $d=1+\rho(n-1)$ , where  $n$ =average number of visits per patient, and  $\rho$  is the patient intraclass correlation. We apply a conservative intraclass correlation of 0.30. The power analysis also takes into consideration the following factors: 1) 18% drop-out as observed in WIN; 2) adjusted 2-sided significance level of 0.025; and 3) 80% power. With these factors, the study is powered to observe a standardized effect of 0.29 and 0.32 difference in mean change in asthma control across intervention groups at 6 months and 12 months, respectively. **Specific Aim 2:** The power analysis examines the intervention effect on 5 asthma outcome measures at 6 and 12 months. Using the same assumptions but with 2-sided  $\alpha=0.005$  to conservatively adjust for multiple comparisons, we will have 80% power to detect a standardized effect of 0.34 and 0.31 between groups at 6 months and 12 months, respectively. **Specific Aim 3:** Power for the economic analysis (costs have greater variability than clinical outcomes) is 81% based on the same effect size, 2-sided  $\alpha$  of 0.05, an effect-cost correlation of -0.1, a difference in cost of \$500 and a willingness to pay (WTP) threshold of \$2500 per year of improved adherence or avoided hospitalization. An increase in the WTP to \$3000 results in 98% power. Thus, the sample size will provide sufficient statistical power for assessment of both clinical and economic evaluations (which requires detecting both effect and cost differences).

**D.11. Data Management:** The Clinical Research Computing Unit will collaborate to finalize CRFs, construct the database, protect its security, perform data entry, review, query and update data; assist with preparation of DSMB reports, and collaborate with biostatisticians as it has for HAP and WIN studies.

**D.12. The Data Safety Monitoring Board** (see Human Subjects) will meet at study start, year 2, and year 5. At these and every 6 months the DSMB will review reports of accrual, baseline comparability between PA and UC groups, adverse events, safety concerns, data quality, maintenance of confidentiality and recommend study modifications and whether the study can continue.

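### The Aim 2 count model makes no provision for extra-Poisson variation within a visit window, so its treatment-by-visit standard errors would be too small if events bunch there

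*Combined protocol and SAP*

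**What the plan says.** D.9 assigns follow-up models by outcome type: "The RE models will be linear, logistic, and log-linear for continuous, binary, and count outcomes, respectively". The purpose of the random effects is given as: "The RE will be included to account for correlated and missing data". Neither the level of the random effects nor the count distribution is stated. The tested quantity is defined by "the treatment-time interaction for a particular visit will be the ITT effect on change since baseline". Site enters through "including site as a fixed effect in all analyses".

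D.9 names a count distribution once, for the baseline comparisons, which rest "on Poisson log-linear regression for count data". The paragraph on Aims 1 and 2 describes the test through the "treatment-6 month visit interaction in the linear RE model (described above) with asthma control as the dependent variable" and does not restate the count model.

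No section mentions overdispersion, a negative binomial form, an observation-level effect, a scale parameter or robust variance. The data-screening paragraph in D.9 covers normality and homoscedasticity but not the dispersion of counts. D.10 plans Aim 2 as five outcomes at two times, each tested two-sided at 0.005.

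**The concern.** Three of the five Aim 2 outcomes are natural counts: prednisone bursts, ED visits and hospitalizations. The tested term compares a patient's events in a later window with the same patient's events at baseline. A patient random intercept largely cancels from that contrast, so what remains is the variance within a patient between windows. A Poisson model fixes that variance at the mean. If events bunch inside a window, the true variance is larger and the reported standard error is too small.

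The plan itself points to two sources of bunching, without giving a size:

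- D.8.1 counts both a new prednisone prescription and an increase in an existing dose as a burst. One exacerbation could therefore give two bursts in one window, and no rule merges events from the same episode.
- D.5 acknowledges seasonal variation and relies on randomization and year-round recruitment to deal with it. These guard against bias but do not remove variance. Patients enrolled at different times reach a given study visit in different seasons, so the visit effects cannot absorb the variation.

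At stake is the error rate of the Aim 2 tests on these outcomes. D.10 sets 0.005 as a deliberately strict level, and understated standard errors would undo part of that protection.

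**Working it through.** **1. The plan's own Aim 2 figures.** Inputs from D.10: 150 per arm, 18% dropout (150 × 0.82 = 123), intraclass correlation 0.30, two-sided α = 0.005 (0.05/10), 80% power.

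δ = (z₀.₉₉₇₅ + z₀.₈₀) × √(2[1 + 0.30(n − 1)]/(123n)), with z-sum 2.807 + 0.842 = 3.649.

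- n = 3: 3.649 × √(2 × 1.6/369) = 0.340 (stated 0.34)
- n = 5: 3.649 × √(2 × 2.2/615) = 0.309 (stated 0.31)

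Both reproduce. They rest on a t-test, so the choice of count model does not move them.

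**2. Event rates.** The only event figures are in D.1.1: in the WIN Study, 52% had ED visits and 31% had hospitalizations in the prior year. Let μ be the mean count per quarter and σ² the patient-level (gamma) variance. With no visit-level variance, 1 − (1 + 4μσ²)^(−1/σ²) equals the yearly proportion. For σ² = 1:

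- ED visits: μ = (1/0.48 − 1)/4 = 0.271
- Hospitalizations: μ = (1/0.69 − 1)/4 = 0.112

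One proportion cannot separate patient-level from visit-level variance. Both are therefore assumed: σ² = 1 or 2, and visit-level gamma variance φ = 0, 0.5, 1 or 2. The rate μ is recalibrated for each pair.

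**3. Simulation.** 1,500 null trials per setting, 150 per arm, five quarterly visits, 18% monotone dropout, site effects omitted. The fitted model was Poisson log-linear with one patient random effect and treatment-by-visit terms. Month-6 results, with ranges over σ² = 1 and 2:

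| Outcome | φ | Model SE / true SE | Type I error at 0.05 | Type I error at 0.005 | 95% CI coverage |
|---|---|---|---|---|---|
| ED | 0 | 1.00-1.02 | 4.3-4.4% | 0.4-0.5% | 96% |
| ED | 0.5 | 0.76-0.90 | 7.7-14.0% | 0.8-2.9% | 86-92% |
| ED | 1 | 0.65-0.77 | 13.2-20.1% | 2.1-6.5% | 80-87% |
| ED | 2 | 0.50-0.66 | 19.9-32.3% | 5.9-16.6% | 68-80% |
| Hosp. | 0 | 1.00-1.01 | 4.2-4.8% | 0.2-0.4% | 95-96% |
| Hosp. | 0.5 | 0.88-0.95 | 5.4-8.9% | 0.4-1.3% | 91-95% |
| Hosp. | 1 | 0.82-0.89 | 7.3-9.9% | 0.7-2.1% | 90-93% |
| Hosp. | 2 | 0.72-0.81 | 10.3-15.9% | 1.5-3.8% | 84-90% |

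Month 12 is similar (ED at φ = 1: SE ratio 0.65-0.77). Monte Carlo error is about 0.2 percentage points at nominal 0.005 and 0.6 at nominal 0.05.

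**4. Hand check.** Averaged over patients, the within-patient variance is μ + φμ²(1 + σ²), against μ under Poisson. The SE ratio is then roughly 1/√(1 + φμ(1 + σ²)). At φ = 1:

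- ED, σ² = 1, μ = 0.308: 1/√1.616 = 0.79 (simulated 0.77)
- ED, σ² = 2, μ = 0.484: 1/√2.452 = 0.64 (simulated 0.65)
- Hospitalizations, σ² = 1, μ = 0.121: 1/√1.242 = 0.90 (simulated 0.89)
- Hospitalizations, σ² = 2, μ = 0.152: 1/√1.456 = 0.83 (simulated 0.82)

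The formula also shows why the rarer outcome suffers less: the excess grows with μ.

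**5. Patient-clustered robust errors on the same fit.** At month 6, over all φ, the SE ratio is 0.93-1.00, with type I error 4.3-7.5% at 0.05 and 0.3-1.3% at 0.005. At month 12 the worst case (ED, σ² = 2, φ = 2) has SE ratio 0.89 and type I errors of 8.4% and 1.5%.

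**6. Second simulation.** With 400 trials per setting, 123 per arm and a patient effect of SD 0.8 on the log scale, ED type I error at nominal 0.05 was 4%, 14% and 16% at φ = 0, 1 and 2. Hospitalizations gave 7% and 13% at φ = 1 and 2. The direction is the same, with less precision.

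**The case against.** The strongest reply is that the plan never says Poisson for follow-up and never says that a patient effect is the only source of extra variance. A negative binomial model with a log link and random effects would also fit the words of D.9. Nor does any section assign the three event outcomes to the count model rather than the binary one. This stands: the Poisson reading is an inference, although D.9's only other use of the log-linear term for counts is the phrase "and on Poisson log-linear regression for count data". The reply does not remove the gap, because a model left open can be chosen after the data are seen. The linear model named under Aims 1 and 2 is tied there to asthma control, so it does not settle how counts are handled.

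The size rests wholly on assumed variances, and the documents report no mean counts or dispersion. That also stands. A reader might infer that the Aim 2 intervals are too narrow as a matter of fact. The documents do not support this: at φ = 0 the planned errors are correct, and at φ = 0.5 with σ² = 1 the hospitalization error is only about 5% too small.

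A reader might also infer that the problem carries into Aim 3, since the same events enter the cost-effectiveness ratios. It does not. Aim 3 uses differences in mean costs and mean outcomes with bootstrap intervals, not standard errors from these models.

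**Conclusion.** The point holds conditionally. Read as Poisson with a patient random effect, the count model gives correct treatment-by-visit standard errors if events are Poisson within patients, and understated ones if they bunch within windows. Bunching is plausible from the plan's own definitions and its remark on seasons, but it is not quantified.

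For φ between 0.5 and 1, the month-6 standard error is about 10-35% too small for ED visits and 5-18% too small for hospitalizations. At φ = 1, the test at 0.005 runs at about 4 to 13 times its nominal level for ED visits (0.0213/0.005 to 0.0653/0.005) and 1.5 to 4 times for hospitalizations (0.0073/0.005 to 0.0213/0.005). Prednisone bursts were not assessed because no rate is given, so these sizes should not be extended to them.

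Aim 1 is unaffected because asthma control is continuous. The sample size and the Aim 2 detectable effects are also unchanged. The change is worth making because it is cheap and is needed whichever count model the investigators intend.

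**What to change.** Add one sentence to D.9. For outcomes analysed as counts (prednisone bursts, ED visits, hospitalizations), either:

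- keep the log-linear random effects model, stating its distribution and the level of its random effects, and base treatment-by-visit tests and intervals on patient-clustered robust standard errors; or
- specify a negative binomial random effects model with a patient random intercept.

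Choose one before the outcome data are seen. Both are standard software options.

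The cost is slightly wider intervals if there is no extra dispersion. Robust errors may stay mildly anti-conservative, at about 4-8% for nominal 0.05 in the settings above. The negative binomial option was not simulated here.

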## D.2. Methods and Procedures

**D.2.1. Summary:** This pragmatic RCT will recruit 300 adults with moderate or severe asthma from clinics serving low-income inner-city neighborhoods, randomizing participants 1:1, stratified by practice, to PAI or usual care (UC) for 6 months of intervention followed by 6 months of observation. We will assess PAI's cost-effectiveness. Secondary aims will assess mediators and moderators of the PAI-asthma outcome relationship. We will explore the awareness and response to PAI with post-study focus groups of providers.

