Eligible consenting patient participants will be randomized 1:1 to PAI or UC. Block randomization with block sizes ranging randomly between 4 and 6 consecutive participants within each site will be employed to ensure that equal numbers of participants are assigned to each of the two groups and are balanced with respect to observed and unmeasured baseline factors. Randomization will be single-blind; study investigators will be blinded to group assignment throughout the study and its analysis. [name], the biostatistician, will generate randomization lists based on the above procedure.

**Participants are adults recruited from clinics serving low-income neighborhoods.** Most asthma studies involve children; adults are relatively understudied. With the WIN and HAP Studies, we established effective recruitment methods and relationships with a variety of clinical practices to recruit and retain adults. Our experience suggests we will recruit patients with significant numbers of hospitalizations and ED visits and other health care costs. An effective intervention will reduce these costs and improve patient health. From HAP, we observed that patients who find a PA most useful will enroll. Very busy, employed, highly educated persons, least likely to benefit from a PA, do not have time to participate and do not enroll.

**PA activities:** Informed by focus groups (D.1.3) and HAP (D.1.4), the PA will facilitate and model administrative tasks to navigate the health system and practice, prepare for visits, carry out medical recommendations, and overcome social and community barriers to accessing care. The PA will coach patients to articulate appointment goals and concern about or lack of understanding of medical advice. We will individualize PA activities surrounding 1) preparation for asthma doctor visits, 2) medical visits attended by the PA, and 3) ensuring understanding, scheduling, and administrative tasks agreed upon by doctor and patient.

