**Exclusion criteria:** 1) Severe psychiatric or cognitive problems (e.g., obvious mania, schizophrenia, significant mental retardation) that make it impossible to understand and carryout PA activities. Formal psychiatric evaluations are outside the scope of this project. However, RCs will be trained to identify patients during screening who do not appear to be mentally competent to carry out study tasks. Individual cases will be reviewed by the PI. In HAP and WIN Studies this has happened in 1-2 instances/study. Each clinical site has mental health facilities for referral of patients. 2) Unable to understand and provide informed consent, 3) Unable to communicate in English or Spanish. 4) Participants of the HAP Study are excluded.

We will not exclude patients with other comorbidities who meet the above inclusion criteria. Patients with comorbidities may benefit most from a PA. Smoking is not an exclusion criterion. Initially, we excluded smokers in WIN, but eliminated this exclusion because it excluded significant numbers of patients, particularly poor patients, who might benefit from the intervention. Although this is a study of asthma patients, the PAI is not necessarily specific to asthma. Thus, defining "pure" asthma, if it were possible, is unnecessary.

**D.4. Recruitment sites** include primary care and asthma-specialty practices in a variety of settings. There are 2 family medicine, 2 general internal medicine, 2 pulmonary and 1 allergy outpatient practice from the University of Pennsylvania Health System; practices at the Philadelphia Veterans Affairs Medical Center; the community-based primary care practice of the Woodland Avenue Health Clinic, a federally qualified health center; and the Episcopal Hospital Comprehensive Health Center, a primary care practice serving mainly Spanish-speaking patients. All sites have a large pool of patients with asthma and serve urban low income and minority patients from the surrounding communities. We have previously recruited from all sites. Having 10 sites, including both specialty and primary care practices, improves the generalizability of the results by asthma severity and patient demographics and ensures adequate enrollment. Eight sites are within walking distance of our office and the last two are easily accessed by public transportation (See Resources). All participating practices will have an orientation meeting prior to the beginning of recruitment.

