**Specific Aim 3 (To estimate the incremental costs and incremental cost-effectiveness (ICE) of PA):** ICE will be assessed by comparing the incremental cost of PA (including both intervention costs, as well as costs of care) relative to UC per outcome, e.g. cost per day asthma control or avoided ED, hospitalization. The ICE will be determined based on differences in direct costs (payer perspective) and also including indirect

costs (societal perspective) and will be calculated based on differences in mean costs for the UC group from those in the PA group, divided by the mean difference in outcomes (asthma control, prednisone bursts, ED visits, hospitalizations, etc.). We also will calculate the incremental cost per quality adjusted life year as estimated from the AQOL. We will estimate statistical error and construct confidence intervals using bootstrap procedures for the incremental cost difference and the incremental cost-effectiveness ratio (ICER).

**Exploratory Aim (Post-study focus groups of providers):** Audio records and notes will be coded into categories emerging from the data by independent coders ([name], [name], [name]) who will achieve inter-coder reliability. Using the Grounded Theory approach, we will then analyze the agreed upon categories, and place them into themes emerging from discussions.

**D.10. Sample size:** We will enroll 300 adults (150 per intervention group). The primary outcome (Aim 1) is asthma control at Visit 3 (6 months) and Visit 5 (12 months). While a clinically meaningful difference in asthma control within-individual is 0.5, we expect the average difference across groups to be smaller. The WIN Study demonstrated a small difference in mean change of  $0.2 \pm 1.1$  in asthma control across intervention groups at Visit 8 (6 months). The effect was neither clinically nor statistically significant. A difference in mean change of 0.32 in asthma control was found in a study with a different focus, but the effect was not statistically significant, probably due to the small sample size.

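### D.9 says the sample size was enlarged for the site analysis, but D.10 contains no site allowance, and 300 participants give low power for small to moderate site differences in effect

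*Combined protocol and SAP*

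**What the plan says.** D.2.1 and D.2.2 randomize individual participants 1:1, stratified by practice. D.4 lists the practices: "Having 10 sites, including both specialty and primary care practices". D.9 puts site into all analyses as a fixed effect, on the ground that the intervention may work differently across practices.

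The D.9 paragraph on the impact of site says that stratification was chosen so that the effect of site can be analysed, and continues: "We have amplified the sample size (D.10) to have a large enough sample to conduct this analysis". It then introduces treatment-by-site interactions as a secondary analysis. If they are statistically significant, a separate treatment effect is to be reported for each site.

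D.10 sets the total: "We will enroll 300 adults (150 per intervention group". For Aim 1 it describes a two-sample t-test with a design effect for visits within patient (intraclass correlation 0.30) and adds: "The power analysis also takes into consideration the following factors: 1) 18% drop-out as observed in WIN; 2) adjusted 2-sided significance level of 0.025", with 80% power. It reports detectable standardized effects of 0.29 (6 months) and 0.32 (12 months). For Aim 2, at a two-sided level of 0.005, it reports 0.34 and 0.31.

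**The concern.** D.9 sends the reader to D.10 for an enlargement that cannot be found there. D.10 has no site-level correlation, no inflation factor for site, no target site difference and no power for an interaction.

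This matters because D.9 makes site-specific reporting depend on a significant interaction. If the test has low power, the usual outcome will be a single pooled effect. A reader who has been told that the sample was enlarged for this purpose may then take the absence of an interaction as informative about primary care, specialty, VA and health-center practices.

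**Working it through.** **1. Reproduce D.10 without any site term.** Inputs from D.10: 150 per arm, 18% drop-out, so 150 × 0.82 = 123 completers per arm; ρ = 0.30; n = 3 visits (6 months) or 5 (12 months); 80% power; two-sided α = 0.025 (Aim 1) or 0.005 (Aim 2).

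Detectable effect = (z₁₋α/₂ + z₀.₈₀) × √(2f/123), with f = [1 + ρ(n − 1)]/n. This gives f = 1.6/3 = 0.533 for 3 visits and 2.2/5 = 0.44 for 5.

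| Aim, time | z sum | Result | Stated | Enrolled per arm needed at the stated effect |
|---|---|---|---|---|
| Aim 1, 6 months | 3.083 | 0.287 | 0.29 | 121/0.82 → 148 |
| Aim 1, 12 months | 3.083 | 0.261 | 0.32 | 82/0.82 → 100 |
| Aim 2, 6 months | 3.649 | 0.340 | 0.34 | 123/0.82 → 150 |
| Aim 2, 12 months | 3.649 | 0.309 | 0.31 | 122/0.82 → 149 |

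Three of the four figures reproduce and use up the planned 150 per arm. The Aim 1 12-month figure does not reproduce. That is a separate discrepancy, and D.10 does not attribute it to site.

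**2. Size of a site.** Assuming 10 equal sites (the documents give no site sizes): 246/10 = 24.6 completers per site, or 12.3 per arm.

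**3. Power of the treatment-by-site test.** The variance of one site's effect is V = 2f/12.3. Three values of f are defensible:
- 1.4 = 2(1 − 0.30): change score, when the unit is the SD at a single visit.
- 1.0: single-visit variance, or the unit is the SD of change itself.
- 0.533: D.10's averaged-visit factor.

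Let τ be the between-site SD of the standardized effect. The documents give none, so 0.2 and 0.3 are assumptions. The test is F on 9 and 246 − 20 = 226 df at 0.05, with noncentrality 10τ²/V. For example, with f = 0.533 and τ = 0.2, V = 0.0867, the noncentrality is 10 × 0.04/0.0867 = 4.6, and power is 25%. The ranges below also cover noncentrality 9τ²/V and sites treated as a random sample.

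| f | 95% half-width, one site (1.96√V) | Power, τ = 0.2 | Power, τ = 0.3 | τ for 80% power |
|---|---|---|---|---|
| 1.4 | 0.94 | about 11% | 20-22% | 0.61-0.71 |
| 1.0 | 0.79 | 13-14% | 27-30% | 0.51-0.60 |
| 0.533 | 0.58 | 23-25% | 49-56% | 0.38-0.44 |

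The like-for-like comparison with the main effect uses D.10's own factor: 0.375/0.287 = 1.3 to 0.439/0.287 = 1.5. Site effects would have to vary by more than the pooled effect that the trial is sized to detect.

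**The case against.** Several points on the other side stand.

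- **What the sentence refers to.** Grammatically, the analysis for which the sample was enlarged is the effect of site. The interaction comes afterwards and is labelled secondary, so low interaction power does not by itself contradict the sentence. The missing allowance does, because D.10 provides for neither.
- **What the reproduction can show.** A reader might infer that the claim is false because 0.29 reproduces without a site term. That goes too far. D.10 fixes 300 and reports the detectable effect, so the arithmetic shows that nothing was held back. It cannot show that 300 was not raised from some smaller number. The supportable statement is that no allowance is documented.
- **A single power figure.** A reader might settle on 11-22% as the power for realistic site differences. The documents supply no between-site SD, so nothing identifies a realistic one. That range also comes from the change-score variance alone; D.10's own factor gives 23-25% and 49-56%. Nor is the required SD simply twice the main effect, because that ratio mixes two variance factors.
- **How a null result would be read.** No section says that a non-significant interaction will be taken as equal effects. D.9 prescribes only what follows a significant one. Primary versus specialty care is also examined as a moderator (Secondary Aim 2, D.8.3) and in D.14. The risk of misreading is real, but it is an inference.

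The primary estimate, its significance level and the enrolment target are unaffected. None of these points supplies the missing allowance.

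**Conclusion.** The point holds in limited form. D.9 claims a property of the sample size that D.10 does not document, and three of D.10's four figures for Aims 1 and 2 are obtained without it. The claim that the sample is large enough fails for the treatment-by-site interaction when differences are small to moderate.

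The power range in the table rests on 10 equal sites, 18% drop-out and assumed between-site SDs. An assumed unequal split lowers power slightly: at f = 1.0 and τ = 0.2 it falls to about 13%. The direction of the conclusion does not depend on the variance chosen, since under all three factors 80% power requires a between-site SD above 0.29. The exact power does depend on it and should be presented only as a range.

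**What to change.** - In D.9, delete the sentence saying the sample size was enlarged. In D.9 or D.10, state that 300 includes no documented allowance for site. If an allowance was in fact made, D.10 should instead show it with its assumptions.
- Label the treatment-by-site interaction and the site-specific estimates exploratory.
- Give the interaction power as a range, with the assumed between-site SD, site sizes and variance stated beside it.
- State that a non-significant interaction test will not be taken as evidence of equal effects across sites.
- Optionally, report the between-site variation in the treatment effect with its interval.

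The cost is wording in two sections, with no change to enrolment or to the primary analysis. The downside is that the plan gives up a favourable statement about its own sample size.
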